6 PATIENT DISPOSITION AND BASELINE CHARACTERISTICS

A two-sided p-value of 0.05 will be used as the significance level for the determination of statistical significance in the statistical tests with the data from patient disposition and baseline characteristics.

6.1 Patient Disposition

Patient disposition will be summarized with the number and percent of patients who were enrolled, received at least one dose of study medication, completed the study, and were withdrawn from the study (including reasons for withdrawals). The proportions of drop-outs will be compared between the Ferriprox group and the deferoxamine group using Fisher’s exact test.

6.2 Demographics

Demographics data such as age, sex, ethnicity, and race will be summarized by treatment group with descriptive statistics (mean, standard deviation, minimum, and maximum) for continuous variables and with frequency tables for discrete variables.

6.3 LIC, Cardiac MRI T2*, and Serum Ferritin at Baseline

The baseline data of LIC, cardiac MRI T2*, and serum ferritin will be summarized using descriptive statistics by treatment group. If there are multiple baseline values, then the value that was measured closest prior to the treatment will consider to be the baseline value.

6.4 Prior and Concomitant Medications

Prior and concomitant medications will be coded and classified by the Anatomical Therapeutic Chemical (ATC) coding scheme of the World Health Organization (WHO), using the WHO Drug Dictionary Format B – March 2018 or newer. The number and percent of patients who took a concomitant medication in each treatment group will be presented using frequency tables.

6.5 Medical History

Medical history for current and historical diagnoses and co-morbidities will be coded using the Medical Dictionary for Regulatory Activities (MedDRA) Version 21.0 or higher and summarized by treatment group. They will be displayed by MedDRA System Organ Class (SOC) and Preferred Term (PT) and current status will be derived as “Resolved” if the stop date is reported and “Ongoing” if the stop date is missing, and will be presented in descending order of the most frequent Ongoing PT.

6.6 Physical Examinations

A physical examination including head, ears, eyes, nose, throat, neck, respiratory system, general appearance, cardiovascular system, abdominal system, skin, and nervous system will be conducted and any clinically significant findings will be recorded on the medical history log (if the findings are of a pre-existing condition) and the medical events log (if the findings are new untoward medical occurrence or worsening of a pre-existing condition that occurs after ICF signing but before dosing).

6.7 Vital Signs, Weight and Height

Vital signs (temperature, resting heart rate, respiration, and blood pressure), weight and height at baseline will be summarized using descriptive statistics by treatment group.

7 EFFICACY ANALYSES

All statistical analyses will be performed using SAS (version 9.3 or higher) on the Windows operating system.

7.1 Primary Efficacy Endpoint

Primary efficacy endpoint is the change from baseline to Week 52 in LIC. Primary efficacy endpoint will be compared between the two treatment groups using an analysis of covariance (ANCOVA) model including treatment variable as the main factor, and overall average transfusional iron input during the study, baseline LIC, and stratification factors (disease category and transfusional iron input in the 3 months prior to baseline) as covariates. The 96.01% $(1 - \alpha)$, where $\alpha = 0.0399$ based on the Pocock’s α spending function for interim analysis) confidence interval (CI) of the difference (Ferriprox minus deferoxamine) in change of LIC from baseline to Week 52 (i.e., Week 52 minus baseline) between the two treatment groups

will be computed. For the demonstration of non-inferiority, the upper limit of the 96.01% CI should be no more than 2 mg/g dw.

The following SAS codes of MIXED procedure will be used to produce the differences in Least Squares (LS) Mean of change in LIC at Month 6 and Month 12 between Ferriprox and deferoxamine groups and the corresponding 96.01% confidence intervals. In the mixed model, AR (1) (autoregressive of order 1) will be used for the covariance structure, and Kenward and Roger's method will be used to estimate the denominator degrees of freedom (SAS model statement option, DDFM = KR).

```

proc mixed data=LIC;
  class patient treat disease prior_iron month
  model LIC_change = treat overall_iron base_LIC disease prior_iron
    month treat*month / noint solution ddfm=kr;
  repeated month / subject=patient(treat) type=ar(1);
  lsmeans treat*month;
  estimate 'Ferriprox - Deferoxamine at Month 6' treat -1 1
    treat*month -1 0 1 0 / cl alpha=0.0399;
  estimate 'Ferriprox - Deferoxamine at Month 12' treat -1 1
    treat*month 0 -1 0 1 / cl alpha=0.0399;
run;

```

Definition of the variables in the statistical model:

LIC_change : Change in LIC from baseline to Week 5
 treat : Ferriprox or Deferoxamine
 month : Duration of treatment in month
 overall_iron : Overall total transfusional iron input (mg/kg/day) during the study
 base_LIC : LIC at baseline
 disease : Sickle cell disease or other anemias
 prior_iron : transfusional iron input in 3 months prior to baseline (≤ 0.3 mg/kg/day or > 0.3 mg/kg/day)

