#### **11.4.1.3 Efficacy Analyses**

##### **Primary Efficacy Endpoint**

The change from baseline to Week 52 in LIC will be compared between the two treatment groups using an analysis of covariance (ANCOVA) model, including treatment variable as the main factor and total transfusional iron input during the study and baseline LIC as covariates. The 95% confidence interval (CI) of the difference (deferiprone minus deferoxamine) in change of LIC from baseline to Week 52 between the two treatment groups will be computed. For the demonstration of non-inferiority, the upper limit of the 95% CI should be no more than 2 mg/g dw.

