7.3 Trend Analysis for LIC, cardiac MRI T2*, and Serum Ferritin

The longitudinal data of LIC, cardiac MRI T2*, and serum ferritin will be analyzed for time trend by using PROC MIXED procedure in SAS. The observed data of LIC, log-transformed cardiac MRI T2*, and serum ferritin will be used in this analysis. The following two statistical models will be fitted:

- Model 1: Efficacy value = Intercept + Treatment + Time + Treatment \times Time
- Model 2: Efficacy value = Intercept + Treatment + Time

Treatment will be treated as a categorical variable, and Time will be the time in month at each time point. Model 1 is the full model with the main effect of Treatment and Time, and the interaction effect of Treatment \times Time. Model 2 is the reduced model with the main effect of Treatment and Time without the interaction term. If the interaction of Treatment \times Time in Model 1 is not significant ($p > 0.05$), the reduced Model 2 will be used as the final model for trend analysis.

The following SAS codes will be used:

```
proc mixed data=efficacy_data;
  class patient treat;
  model measure = treat month treat*month / solution ddfm=kr;
  repeated / subject=patient(treat) type=ar(1);
run;
```

Definition of the variables in the statistical model:

measure: LIC or log-transformed cardiac MRI T2*, or SF
treat : Ferriprox or Deferoxamine
month : Duration of treatment in month

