7.4 Subgroup Analysis

The comparison of the two treatment groups for the primary and secondary efficacy endpoints will be performed by disease type. The same ANCOVA models without disease factor as used in the main analyses will be used.

- Patients with sickle cell disease (SCD) only
- Non- SCD patients.

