7.6 Exploratory Analysis

The following success criteria in LIC were used for the submission of Exjade’s NDA.

LIC at Baseline	Success, if LIC at the last measure is
2 to < 7 mg Fe/g dw	1 to < 7 mg Fe/g dw
≥ 7 to < 10 mg Fe/g dw	1 to 7 mg Fe/g dw
≥ 10 mg Fe/g dw	Decrease in LIC ≥ 3 mg Fe/g dw

The success rates for Ferriprox and deferoxamine groups will be calculated based on these success criteria and will be compared using Fisher’s exact test. It is noted that there should be no patients in the first category of 2 to < 7 mg Fe/g dw at baseline LIC because one of the inclusion criteria for this study is baseline LIC >7 mg/g dw (measured by MRJ).

In addition to the statistical analyses that have been specified in the SAP, any other exploratory analyses will be performed, if warranted, as post hoc analyses.

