9.3 Transfusional Iron Input

It is noted that transfusional iron input (mg/kg/day) for the 3 months prior to baseline, which is one of the stratification factors of randomization in this study, has been calculated, for example, as follow:

Assumption: 1 mg iron / 1 mL packed Red Blood Cells (pRBCs)

Type of transfusion	Volume of blood transfused (mL)	Average mean hematocrit of pRBC transfused (%) for the site	If partial or exchange transfusions		Iron in pRBC (volume blood transfused*mean hematocrit transfused – volume blood removed*mean hematocrit removed)
			Volume of blood removed (mL)	Average mean hematocrit of pRBC removed (%) for the site (as we do not collect hematocrit, we use hemoglobin*3 = hematocrit as assumption)	
Simple	1200	65			780
Exchange	1250	65	1016	80	0
Partial exchange	2500	65	1000	80	825
Simple	1000	65			650
				Total iron transfused	2255 mg
				Body weight at baseline	54 kg
				3 months*30.5 days	91.5 days

Hence, transfusional iron input (mg/kg/day) for the 3 months = $2255 \text{ mg} / 54 \text{ kg} / 91.5 \text{ days} = 0.46 \text{ mg/kg/day}$.

Transfusional iron input will be calculated monthly during the study in the same way above. Overall total transfusional iron input (mg/kg/day) during the study will be calculated by summing up monthly transfusional iron input. As the total transfusional iron input depends on the length of time a patient remains in the study, the total transfusional iron input will be divided by the total number of days involved in the months where blood transfusion data was obtained and will be compared between the two treatment groups; the same data will be used for the ANCOVA.

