		Treatment		
	Deferiprone	Deferoxamine		
N	xxx	xxx		
		Mean ± SD (Min, Max)	Mean ± SD (Min, Max)	P-value (T-test)
Weight (kg)	xx.x ± xx.x (xx, xx)	xx.x ± xx.x (xx, xx)	0.xxxx	
Height (cm)	xxx.x ± xxx.x (xxx, xxx)	xxx.x ± xxx.x (xxx, xxx)	0.xxxx	

§For patients who had separate screening and baseline visits, height was measured only at screening

Data source: 16.2.7 Listing of vital signs including height and weight

Table 14.2.1.1 LIC at each assessment

		Treatment		
		Deferiprone	Deferoxamine	
N		xxx	xxx	P-value (T-test)
	Visit	Mean \pm SD (Min, Max)	Mean \pm SD (Min, Max)	
LIC (mg/g dw)	Baseline	xx.x \pm xx.x (xx.x, xx.x)	xx.x \pm xx.x (xx.x, xx.x)	0xxxx
	Month 6	xx.x \pm xx.x (xx.x, xx.x)	xx.x \pm xx.x (xx.x, xx.x)	0xxxx
	Month 12	xx.x \pm xx.x (xx.x, xx.x)	xx.x \pm xx.x (xx.x, xx.x)	0xxxx

Data source: 16.2.13 Listing of LIC

Table 14.2.1.2 Change in LIC at each follow-up assessment

		Treatment		
Test	Visit	Deferiprone	Deferoxamine	
N		xxx	xxx	P-value (T-test)
Change in LIC (mg/g dw) Mean \pm SD (Min, Max)	Month 6	xx.x \pm xx.x (xx.x, xx.x)	xx.x \pm xx.x (xx.x, xx.x)	0xxxx
	Month 12	xx.x \pm xx.x (xx.x, xx.x)	xx.x \pm xx.x (xx.x, xx.x)	0xxxx

Data source: 16.2.13 Listing of LIC

Table 14.2.1.3 LS Means of change in LIC from ANCOVA model at each follow-up assessment

		Treatment			
		Deferiprone	Deferoxamine	Deferiprone minus Deferoxamine	96.01% C.I.
N		xxx	xxx	xxx	
	Visit	LS Mean \pm SE	LS Mean \pm SE	LS Mean \pm SE	
LIC (mg/g dw)	Month 6	xx.x \pm xx.x	xx.x \pm xx.x	xx.x \pm xx.x	(xx.x, xx.x)
	Month 12	xx.x \pm xx.x	xx.x \pm xx.x	xx.x \pm xx.x	(xx.x, xx.x)

Data source: 16.2.13 Listing of LIC

Table 14.2.1.4 Trend analysis for LIC over time

	Deferiprone	Deferoxamine	Deferiprone minus Deferoxamine	P-value
Slope: Mean \pm SE	xx.x \pm xx.x	xx.x \pm xx.x	xx. x \pm xx.x	0.xxxx

Data source: 16.2.13 Listing of LIC

Table 14.2.1.5 Success rate in LIC based on the submission of Exjade's NDA.

	Treatment		
	Deferiprone	Deferoxamine	P-value (Fisher's exact test)
Success rate	xx.x %	xx.x%	0.xxxx

Data source: 16.2.13 Listing of LIC

Table 14.2.2.1 Cardiac MRI T2* at each assessment

		Treatment		
		Deferiprone	Deferoxamine	
N		xxx	xxx	P-value (T-test)
	Visit	Mean \pm SD (Min, Max)	Mean \pm SD (Min, Max)	
Cardiac MRI T2* (ms)	Baseline	xx.x \pm xx.x (xx.x, xx.x)	xx.x \pm xx.x (xx.x, xx.x)	0.xxxx .
	Month 6	xx.x \pm xx.x (xx.x, xx.x)	xx.x \pm xx.x (xx.x, xx.x)	0.xxxx
	Month 12	xx.x \pm xx.x (xx.x, xx.x)	xx.x \pm xx.x (xx.x, xx.x)	0.xxxx

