Pregnancy test: Positive		
Patient ID	XXXXXX XXXXXX XXXXXX XXXXXX	XXXXXX XXXXXX XXXXXX XXXXXX

Data source: 16.2.17 Listing of pregnancy

Table 14.3.8.1 The number and percent of patients who had compliance $\leq 80\%$ or $\geq 120\%$ during the study

	Treatment					
	Deferiprone		Deferoxamine		P-value (Fisher's exact test)	
Compliance	N	Percent	N	Percent		
$< 80\%$	xx	xx.x%	xx	xx.x%	0.xxxx	
$> 120\%$	xx	xx.x%	xx	xx.x%	0.xxxx	

Data source: 16.2.24 Listing of compliance

Table 14.5.1 Transfusional iron input (mg/kg/day) during the study

	Treatment					
	Deferiprone		Deferoxamine		P-value (T-test)	
	N	Mean \pm SD (Min, Max)	N	Mean \pm SD (Min, Max)		
Transfusional iron input (mg/kg/day)	xxx	xx.x \pm xx.x (xx, xx)	xxx	xx.x \pm xx.x (xx, xx)	0.xxxx	

Data source: 16.2.32 Listing of transfusion information

Table 14.6.1 Summary of total daily dose

	Treatment				
	Deferiprone		Deferoxamine		
	N	Mean \pm SD (Min, Max)	N	Mean \pm SD (Min, Max)	
Total daily dose (mg/kg/day)	xxx	xx.x \pm xx.x (xx, xx)	xxx	xx.x \pm xx.x (xx, xx)	

Data source: 16.2.22 Listing of dose verification

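### Every planned confidence interval (CI) read against the 2 mg/g margin adjusts for transfusional iron received after randomisation; one prespecified sensitivity CI without that covariate, and a rule for reading it, should be added.

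*SAP*

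**What the plan says.** Protocol 11.4.1.3 defines the primary ANCOVA with "total transfusional iron input during the study and baseline LIC as covariates". SAP 7.1 keeps on-study iron, expresses it as an average rate, and adds the two stratification factors, so that its covariates are "overall average transfusional iron input during the study, baseline LIC, and stratification factors". The SAS code carries it as overall_iron. Non-inferiority is shown if the upper 96.01% limit for Ferriprox minus deferoxamine is at most 2 mg/g dw.

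The repeats keep the covariate:

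- **Subgroups (SAP 7.4):** "The same ANCOVA models without disease factor as used in the main analyses will be used".
- **Per-protocol (SAP 4.2):** the primary LIC analysis is repeated and no other model is given.
- **Sensitivity (SAP 7.5):** one analysis changes the imputation. The other restricts the patients to those with at least 6-month LIC data.

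The LIC analyses without the covariate are these:

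- **Trend model (SAP 7.3):** "model measure = treat month treat*month / solution ddfm=kr". Its table reports slopes with SEs and a p-value.
- **t-tests:** Table 14.2.1.1 and "Table 14.2.1.2 Change in LIC at each follow-up assessment" report means, SDs and a p-value.
- **Responder rates (SAP 7.6):** these "will be calculated based on these success criteria and will be compared using" Fisher's exact test.

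None of these tables has a CI column set against 2 mg/g.

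On iron input itself, SAP 9.3 says that it "will be compared between the two treatment groups; the same data will be used for the ANCOVA". The shell "Table 14.5.1 Transfusional iron input (mg/kg/day) during the study" gives a t-test. Neither document says how the primary result would be read if treatment might have caused a difference.

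**The concern.** Adjusting for a baseline variable leaves the meaning of the treatment comparison intact. Adjusting for something that happens after randomisation does so only if treatment does not influence it. Here staff and patients know the assigned drug. The protocol records the type and volume of each transfusion but fixes no regimen, and continuing need is left to the investigator's judgement (Protocol 4.2 and 5.1). An effect of assignment on transfusion is therefore possible, though not demonstrated.

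If there were such an effect, the adjusted difference would omit the part of the treatment effect on LIC that runs through transfusion. The omission could favour either arm. Since every CI judged against the margin carries the same adjustment, agreement among the planned analyses would not reveal whether the non-inferiority conclusion depends on it.

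**Working it through.** **Plan figures first.** SAP 3.7: 0.05 × ln(1 + 1.718 × 0.71) = 0.0399, so the CI level is 96.01%. This reproduces. Protocol 18.4: 79 and 158 patients, margin 2, SD 4, one-sided 0.025, two-sample t-test, gives 95.1% power (stated 95.0%). This also reproduces, and it uses no covariate. For the interim analysis (142 and 71 patients, two-sided 0.0399) the same method gives 91.4%, where SAP 3.2 states 89%. That gap does not affect this point.

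**1. CI without the covariate.** Inputs: 142 and 71 patients, SD 4.

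- k = √(1/142 + 1/71) = 0.1453; SE = 4 × 0.1453 = 0.581.
- t(211 df, two-sided 0.0399) = 2.068; half-width = 1.20.
- To pass, the point estimate must be at most 2 − 1.20 = 0.80 mg/g.

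**2. Assumed slope of LIC on iron input.** The documents give a rise of 5 mg/g per year without chelation, but not the iron rate behind it. Assuming 0.3 to 0.5 mg/kg/day gives 5/0.5 = 10 to 5/0.3 = 16.7 mg/g per mg/kg/day. Chelation, and dose increases triggered by iron input, could flatten this.

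**3. CI with the covariate.** The between-patient SD of iron input is assumed to be 0.10 to 0.15 mg/kg/day.

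- R² = (slope × SD of iron / 4)² = (10 × 0.10/4)² = 0.0625 to (16.7 × 0.15/4)² = 0.391.
- SE = 0.581 × √(1 − R²) = 0.563 to 0.454; half-width 1.16 to 0.94.
- To pass, the estimate must be at most 0.84 to 1.06.
- Dropping the covariate enlarges the SE by a factor of 1.03 to 1.28, less whatever the prior-iron stratum recovers.

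**4. Shift if treatment changes iron input.** Shift = slope × treatment-caused arm difference.

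| Case | Arm difference (mg/kg/day) | Shift (mg/g) | Share of margin |
|---|---|---|---|
| Low, assumed | 0.02 | 10 × 0.02 = 0.20 | 10% |
| High, assumed | 0.05 | 16.7 × 0.05 = 0.83 | 42% |
| Mild | 0.0041 | 0.04 to 0.07 | 2 to 3% |

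The mild case uses the volumes in the SAP 9.3 example. The exchange there nets to zero iron. Given as a simple transfusion it would add 1250 × 0.65 = 812.5 mg, or 812.5/54/365 = 0.041 mg/kg/day over a year. If 10% of one arm had one such switch, the arm difference would be 0.0041.

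**5. Disagreement by chance.** With no effect of treatment on transfusion, the two estimates still differ with SD = slope × SD of iron × k = 0.15 (10, 0.10) to 0.36 (16.7, 0.15) mg/g. In simulations with 142 and 71 patients, total SD 4 and no true difference, both models were unbiased. They disagreed on pass or fail in about 3 to 8% of trials across these inputs.

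**The case against.** The strongest case on the other side has four parts.

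**The covariate is deliberate and may be the right one.** It has been in the protocol throughout, and the margin rationale assumes patients transfused at the same rate. A comparison at equal iron input arguably matches that rationale. This stands, and it is a good reason to leave SAP 7.1 as primary.

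**Imbalance is already handled.** A reader might infer that the plan ignores an arm difference in iron input. It does not: SAP 9.3 feeds the same data into the ANCOVA, which adjusts for the difference. What is missing is narrower, namely a rule for reading the result when treatment may have caused the difference.

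**Rough checks exist.** A reader might also infer that nothing planned speaks to the result without the covariate. That goes too far.

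- A crude CI can be formed by hand from the means and SDs in Table 14.2.1.2.
- If the interaction model is kept, the slope difference and SE in Table 14.2.1.4, multiplied by 12 months, give another.
- The SAP 7.1 code also prints the fitted iron coefficient, which can be multiplied by the arm difference in Table 14.5.1.

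Each has limits. The first lacks baseline and stratum adjustment. The second assumes linear change, omits strata, and needs an interaction with p at or below 0.05, which is unlikely when the arms perform alike. The third is not in any table shell. None is a planned CI against the margin.

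**The size is assumed.** This also stands. The documents give no arm difference in iron input and no slope in chelated patients. A disagreement between the two models would not by itself prove that treatment changed transfusion.

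**Conclusion.** The omission is confirmed from the text: no planned CI against 2 mg/g adjusts for baseline LIC and strata without also adjusting for post-randomisation iron, and no rule covers a difference that treatment may have caused.

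It would be tempting to conclude that the primary analysis is biased or that non-inferiority could be falsely declared. The documents do not support that. They show no effect of treatment on transfusion, and without one the SAP 7.1 estimate is unbiased and more precise. With one, the direction is open and the size is not fixed by the documents. It is 0.2 to 0.8 mg/g under the assumed slope of 10 to 17 and arm difference of 0.02 to 0.05 mg/kg/day, and below 0.1 mg/g in the mild case. The upper end matters against an allowance of about 0.8 to 1.06 mg/g for the point estimate; the mild case does not.

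This is an unexamined dependency of the deciding CI. It is worth closing because doing so is cheap, not because harm has been shown. It does not extend to cardiac T2* or ferritin as a decision issue, since neither has a margin.

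**What to change.** Keep SAP 7.1 as the primary analysis. In SAP 7.5:

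1. Add one LIC sensitivity analysis that repeats the model without overall_iron. The remaining terms are treatment, baseline LIC, disease category, prior-iron stratum, month and treatment by month.
2. Report its 96.01% CI against 2 mg/g beside the primary CI.
3. State in advance that a non-inferiority conclusion that differs between the two models will be reported as dependent on the covariate. It is then read together with Table 14.5.1, allowing for chance imbalance and for the wider CI.

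The same run for cardiac T2* and ferritin is optional and would be descriptive only.

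**Cost.** This is a SAP revision, made before comparative results are seen. Protocol 11.4 already leaves further sensitivity analyses to the SAP, so the protocol text need not change. It takes one more model run on data already collected. The added CI will be wider (SE about 3 to 28% larger under the assumed inputs), so it may occasionally miss the margin by chance when the primary CI meets it. Planned power did not rely on the covariate: Protocol 18.4 uses a two-sample t-test with SD 4, and at 142 and 71 patients that calculation gives 91.4% without it.

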**Sample Size:**

Three hundred (300) male and female patients will be enrolled into the study. In a randomized study of two iron chelators for the treatment of iron overload in patients with sickle cell disease ([Vichinsky E et al. 2007](#)), mean  $\pm$ SD reductions of  $4.0 \pm 1.5$  mg/g dw and  $4.5 \pm 2.0$  mg/g dw in LIC, as measured by SQUID, were observed (Figure 1 of the article, numerical values obtained from the authors) in patients from the baseline LIC categories of  $>7$ - $14$  mg/g dw or  $>14$  mg/g dw after they were treated with 35-50 mg/kg or  $\geq 50$  mg/kg of deferoxamine respectively, for 52 weeks. Assuming the same mean reduction in LIC for deferiprone but a higher SD of  $\pm 4.0$  mg/g dw for both treatments due to possibly higher variability associated with MRI measurement, the sample size of 300, with  $>80\%$  being patients with sickle cell disease, will provide over 95% power for demonstrating non-inferiority of deferiprone to deferoxamine in patients with sickle cell disease.

The sample size estimate is based on a non-inferiority margin of 2 mg/g dw for the reduction of LIC and an alpha of 0.05, two-sided (or an alpha of 0.025, one-sided). It has been reported that in a typical patient with thalassemia major, the LIC could increase by 5 mg/g dw after 1 year without chelation therapy. As the cause of iron overload is the same in thalassemia and sickle cell disease, the same increase in LIC may be expected if patients with sickle cell disease are transfused at the same rate and not treated with a chelator. Hence, the difference in reduction of LIC between deferoxamine therapy and a placebo (effect size) can be estimated to be 9 (i.e., 4 – (-5)) mg/g dw. This means that the non-inferiority margin of 2 mg/g dw would be about 20% of the effect size.

With the enrolment of 300 patients, there is a greater than 99% chance (power) of occurrence of at least 1 adverse event with an anticipated incidence rate of 2%, or greater than 95% chance for an anticipated incidence rate as low as 1%.

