### 11.2.4 Determination of Sample Size

Three hundred (300) male and female patients will be enrolled into the study. In a randomized study of two iron chelators for the treatment of iron overload in patients with sickle cell disease (Vichinsky et al., 2006), mean  $\pm$ SD reductions of  $4.0 \pm 1.5$  mg/g dw and  $4.5 \pm 2.0$  mg/g dw were observed (Figure 1 of the article, numerical values obtained from the authors) in patients from the baseline LIC categories of  $>7$ - $14$  mg/g dw or  $>14$  mg/g dw after they were treated with 35-50 mg/kg or  $\geq 50$  mg/kg of deferoxamine respectively, for 52 weeks. Assuming the same mean reduction in LIC for deferiprone but a higher SD of  $\pm 4.0$  mg/g dw for both treatments due to possibly higher variability associated with MRI measurement, the sample size of 300, with  $>80\%$  being patients with sickle cell disease, will provide over 95% power for demonstrating non-inferiority of deferiprone to deferoxamine in patients with sickle cell disease.

The sample size estimate is based on a non-inferiority margin of 2 mg/g dw for the reduction of LIC and an alpha of 0.05, two-sided (or an alpha of 0.025, one-sided, Appendix 18.5). It has been reported that in a typical patient with thalassemia major, the LIC could increase by 5 mg/g dw after 1 year without chelation therapy. As the cause of iron overload is the same in thalassemia and sickle cell disease, the same increase in LIC may be expected in patients with sickle cell disease who are transfused at the same rate and not treated with a chelator. Hence, the difference in reduction of LIC between deferoxamine therapy and a placebo (effect size) can be estimated to be 9 (i.e., 4 – (-5)) mg/g dw. This means that the non-inferiority margin of 2 mg/g dw would be about 20% of the effect size.

With the enrolment of 300 patients, there is also greater than 99% chance (power) of occurrence of at least 1 adverse event with an anticipated incidence rate of 2%, or greater than 95% chance for an anticipated incidence rate as low as 1%.

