However, patient's recruitment in this study has proceeded at a very slow pace and despite all our efforts over the past 4 years, the goal of enrolling a total of 300 patients has not been reached. A total of 213 patients (142 patients for Ferriprox and 71 patients for deferoxamine) are projected to have either completed the study or been withdrawn from the study by November 30, 2018. An interim analysis is planned to be performed on the data of these 213 patients. Based on the same values of non-inferiority margin and SD of the LIC measurement, but an α level of 0.0399, two-sided (Pocock's α spending method, see section 3.7 for details), this sample size (213 patients) will provide 89% power to demonstrate non-inferiority of Ferriprox to deferoxamine in this interim analysis, assuming no real difference in efficacy between the two treatments. For the subgroup analysis of only patients with sickle cell disease, the power will be 82% as there are 178 SCD patients (119 patients for Ferriprox and 59 patients for deferoxamine), which is approximately 84% of 213 patients. With the safety data of 213 patients, there is 98% chance (power) of occurrence of at least 1 SAE with an anticipated incidence rate of 2%, or 88% chance for an anticipated incidence rate of as low as 1%.

During this interim analysis, while patient enrollment has been put on hold, there will still be 17 patients who are on-going with their assigned drug treatment. All are projected to have completed the study by October, 2019. If the results of the interim analysis lead to the conclusion of non-inferiority of Ferriprox to deferoxamine, considerations will be given on early termination of the study, to avoid unnecessary exposure of patients to a clinical trial that has reached its objectives. The data from those patients up to the time of

study closure will be added to the interim dataset for the final statistical analysis of the study based on the same statistical analyses in this SAP.

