5. HANDLING OF MISSING DATA

In the efficacy analyses, for patients who were terminated from the study prior to Month 12, if their last efficacy measures were obtained within 30 days of Month 12, the data obtained will be treated as the Month 12 data. For early termination that occurred outside this window, the last observation carried forward (LOCF) method will be used to fill the missing data when the early termination was not caused by worsening of disease conditions or inadequate efficacy of the drug. For early termination due to worsening

of disease conditions or inadequate efficacy of the drug, as judged by assessing the AE log, the “worst value” method will be used. That is, the worst value of all patients from the corresponding treatment group will be used to impute the missing data at that time point. For missing data due to missed visit, the LOCF method will be used to fill the void.

For safety data analysis, no imputation will be performed on the missing data, and analysis will be based on observed cases (OC).

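### The primary LIC model forces one residual variance on Months 6 and 12, so the deciding Month 12 interval is too narrow if the Month 6 spread is smaller

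*SAP*

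**What the plan says.** Protocol 11.4.1.3 compares the change in LIC from baseline to Week 52 "using an analysis of covariance (ANCOVA) model, including treatment variable as the main factor", with iron input during the study and baseline LIC as covariates. An analysis of that form estimates its error variance from Week 52 data only.

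The text of SAP 7.1 also calls the primary analysis an ANCOVA of the Week 52 change. The code beneath it is different: a PROC MIXED model of the changes at Months 6 and 12, for which "AR (1) (autoregressive of order 1) will be used for the covariance structure". The code matches that text: "repeated month / subject=patient(treat) type=ar(1"). It contains no heterogeneous or unstructured type and no GROUP= or EMPIRICAL option. Degrees of freedom are by Kenward-Roger. Non-inferiority is declared if the upper limit of the 96.01% interval for deferiprone minus deferoxamine is no more than 2 mg/g dw.

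SAP 5 fills missing values in two ways. For most early terminations and for missed visits, "the last observation carried forward (LOCF) method will be used to fill the missing data". For withdrawals due to worsening or inadequate efficacy, "the worst value of all patients from the corresponding treatment group will be used to impute the missing data at that time point". The sensitivity analyses in SAP 7.5 vary the imputation and the patient set, not the covariance structure. SAP 7.2 reuses the LIC code for cardiac T2*.

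**The concern.** In PROC MIXED, TYPE=AR(1) is the homogeneous form: one variance and one correlation. With only two visits it is the same as compound symmetry, so the autoregressive part adds nothing and what remains is the equal-variance constraint. The Month 12 standard error then rests on the average of the Month 6 and Month 12 residual variances, although the comparison concerns Month 12 alone.

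If patients' changes are less spread out at Month 6 than at Month 12, the deciding interval is too narrow and false non-inferiority becomes more likely than the 0.020 per tail that the SAP allots. If they are more spread out at Month 6, the interval is too wide and only power suffers. Kenward-Roger adjusts small-sample inference given the chosen structure; it does not correct a wrong one. The point estimate is essentially unaffected.

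**Working it through.** **Inputs.** Two-sided alpha 0.0399 (SAP 3.7), so z = 2.0548 and 0.020 in the deciding tail. Margin 2 mg/g dw and SD 4.0 in both arms (SAP and protocol sample-size text). Patients 142 and 71 (SAP sample-size text). The SD of 4.0 is taken as the Month 12 residual SD. No Month 6 SD is given.

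**Baseline figures.** SE = 4.0 × sqrt(1/142 + 1/71) = 0.581. Half-width = 2.0548 × 0.581 = 1.195. The largest observed difference that still passes is 2 − 1.195 = 0.81 mg/g dw. Power at no true difference is Φ(2/0.581 − 2.0548) = 91.7% (91.4% with the t distribution). The SAP says "this sample size (213 patients) will provide 89% power to demonstrate non-inferiority"; that figure does not reproduce from its stated inputs, but the gap is a separate matter and does not affect this point.

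**Effect of the constraint.** With two nearly complete visits, the fitted variance is (s6² + s12²)/2 while the correct one is s12². With r = s6/s12:

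- SE factor k = sqrt((1 + r²)/2)
- one-sided error = 1 − Φ(2.0548 × k)
- largest passing difference = 2 − 1.195 × k

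**Plausible values of r.** The protocol cites SDs of 1.5 and 2.0 for the 52-week change on deferoxamine and raises them to 4.0 "due to possibly higher variability associated with MRI measurement". Let b be the part of the Month 12 variance of 16 that grows with time and f the fraction of b present at Month 6. Then r = sqrt((16 − b(1 − f))/16). f = 1/2 means the growing variance is halved at Month 6; f = 1/4 means its SD is halved. Case 1 lets the whole cited variance grow. Case 2 allows for those SDs describing reductions "in LIC, as measured by SQUID, were observed", and treats half the cited variance as constant SQUID error.

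| Case | b | f | r | k | one-sided error | passing difference |
|---|---|---|---|---|---|---|
| 1 | 2.25 | 1/2 | 0.964 | 0.982 | 0.0218 | 0.83 |
| 1 | 2.25 | 1/4 | 0.946 | 0.973 | 0.0228 | 0.84 |
| 1 | 4.00 | 1/2 | 0.935 | 0.968 | 0.0233 | 0.84 |
| 1 | 4.00 | 1/4 | 0.901 | 0.952 | 0.0252 | 0.86 |
| 2 | 1.125 | 1/2 | 0.982 | 0.991 | 0.0208 | 0.82 |
| 2 | 1.125 | 1/4 | 0.973 | 0.987 | 0.0213 | 0.82 |
| 2 | 2.00 | 1/2 | 0.968 | 0.984 | 0.0216 | 0.82 |
| 2 | 2.00 | 1/4 | 0.952 | 0.976 | 0.0224 | 0.83 |
| Equal spread | – | – | 1 | 1 | 0.0200 | 0.81 |
| Larger at Month 6 | – | – | 1.1 | 1.051 | 0.0154 | 0.74 |

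The error reaches 0.025 when k = 1.960/2.0548 = 0.954, that is at r of about 0.905. At r = 1.1, power falls from 91.7% to 90.0%.

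**Effect of the imputation rules on r.** If a share p of patients have Month 6 values carried to Month 12, the Month 12 variance (in units of s12²) becomes (1 − p) + p·r². With p = 20%, r moves from 0.90 to 0.92, or from 0.96 to 0.97. If a share q receive a worst value d SDs above the mean, having withdrawn after the Month 6 scan, it becomes (1 − q) + q(1 − q)d². With q = 2% and d of 2 to 3, r moves from 1 to 0.97 to 0.93. The two rules pull in opposite directions and the net result is unknown.

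**Simulation.** At a true difference of 2.0, with 40,000 runs, two covariates and an assumed between-visit correlation of 0.6, the AR(1) rule passed 0.0246 of trials at r = 0.90, 0.0217 at 0.96, 0.0199 at 1 and 0.0153 at 1.1; the Month 12-only ANCOVA passed 0.0194. A second simulation (12,000 runs per scenario, SAP fixed effects, correlation 0.7) gave 0.0303 at r = 0.8 and 0.0376 at r = 0.7, with the Week 52 ANCOVA at 0.0196 and 0.0209. Lowering the correlation to 0.4 at r = 0.7 made no material difference (0.0378).

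**The case against.** The strongest reply is that no error is shown from the documents. Harm requires r below 1, no Month 6 SD is given, and the protocol's reason for raising the SD to 4.0 is measurement variability, which would be much the same at both visits and favours r near 1. The r of 0.90 is the extreme of the cases above: it needs the larger cited SD, no measurement error in it, and its SD rather than its variance halved at Month 6. Against a margin of 2, a passing difference of 0.82 to 0.86 instead of 0.81 is small. All of this stands, and it is why the likely effect is called modest.

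Table 14.2.1.2 will show the raw SDs of change at both months, and in simulation raw ratios of 0.92 and 1.08 went with residual ratios of 0.90 and 1.1. A reader could therefore notice a marked departure. That is useful but is no substitute for a pre-specified interval: choosing the structure after seeing those SDs would be data-driven.

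A repeated-measures model is not foreign to the plan, since Protocol 11.4.1.3 foresees a mixed model for time trend. The point is not the mixed model but its equal-variance constraint.

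The serum ferritin code in SAP 7.2 also uses AR(1), over four visits, where it constrains the correlations as well. That has not been quantified here but should be looked at in the same revision.

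**Conclusion.** The concern holds, conditionally. The SAP makes the deciding Month 12 interval depend on an unstated and untested assumption that residual spread is equal at Months 6 and 12. For r of 0.90 to 0.98 the standard error is about 1% to 5% too small and the one-sided error is 0.021 to 0.025 instead of 0.020. At about r = 0.905 the gain from reducing alpha from 0.05 to 0.0399 is fully used up. At r = 1 nothing changes, and at r = 1.1 the test is conservative with a power loss under two percentage points.

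These figures rest on a Month 12 residual SD of 4.0, 142/71 patients, nearly complete two-visit data after imputation, and assumed values of r. If all the variance of change grew in proportion to time, r would be about 0.71 and the error about 0.038, but that leaves no room for constant measurement error and should be read as an outer bound. The case for changing the plan is that validity for any r can be had at almost no cost.

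**What to change.** In the SAP 7.1 code, replace TYPE=AR(1) with TYPE=UN and amend the sentence describing the structure. Alternatively, make the protocol's Week 52 ANCOVA the source of the deciding interval. Carry the change into the code reused for cardiac T2* in SAP 7.2, and reconsider the ferritin code at the same time.

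For LIC and T2* the cost is one extra covariance parameter (three instead of two). If r is in fact 1, the Month 12 interval widens by about 0.2% to 0.3%, through fewer degrees of freedom. There is also an administrative cost: the SAP's approval dates (3 and 5 December 2018) fall after the 30 November 2018 data cut-off and the trial is open-label, so the change needs a dated amendment before database lock, with a rationale that does not draw on the data.
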